## E3 Study Drug

#### 3.a Description

Naltrexone

#### 3.b Treatment Regimen

Low dose naltrexone at 3mg PO daily.

### 3.c Method for Assigning Subjects to Treatment Groups

N/A: open-label, non-randomized, uncontrolled study

#### 3.d Preparation and Administration of Study Drug

Will be compounded by a compounding pharmacy.

#### 3.e Subject Compliance Monitoring

Will be reviewed at regular follow-up visits at 0,3,6 and 12 months.

#### 3.f **Prior and Concomitant Therapy**

Low-dose naltrexone, 3mg orally to be taken daily, will be prescribed. They will be continued on their other treatment medications for lichen planopilaris (LPP) and frontal

fibrosing alopecia (FFA) during the study period without increasing dose. During the study period, other LPP and FFA medications may be decreased in dose or discontinued, but will not be increased or added. This will allow the investigators to analyze the specific benefit of naltrexone.

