## E Study Design

#### E1 Overview or Design Summary

Uncontrolled open-label prospective study

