# G Statistical Plan

Longitudinal data from time points at 0,3,6 and 12 months will be analyzed for each component of the data collection form, including components of the patient assessment of itch and burning/pain (each on a 0-10 point scale), physician assessment for erythema and scale (each on a 0-3 scale) as well as longitudinal comparisons of measurement of the scalp involvement (distance in cm from the glabella to hairline in FFA, and area of scarring/redness/scaling in cm2 for LPP). See below for data collection form.

We predict that oral low-dose naltrexone would lead to approximately 2-3 point decrease in each of the 0-10 point patient assessments (itch and burning/pain) and a 1-2 point decrease in each of the 0-3 point physician assessments (erythema and scale). We expect the areas of scalp involvement to remain stable over the analysis period.

Patient characteristics will be summarized using descriptive statistics. The longitudinal outcomes will be analyzed using mixed model analysis to account for the correlation of measures from the same subject. Time effect will be assessed and contrasts will be used to compare mean difference between any two time points of interest. All statistical tests will be two-sided with a significance level of 0.05 and performed with SAS 9.4. Careful attention will be paid to ensuring that data satisfy assumptions required of a particular analytic strategy. When required assumptions are violated, we will explore the use of data transformations and potentially, perform some analyses using non-parametric or semi-parametric methods based on the rank of some variables.

Data on the quantitative effect size of naltrexone for LPP/FFA is limited, but based on clinical experience and descriptive case studies, we would expect patients to start at a 4-5/10 on the itch/pain/burning scales, and predict that it could decrease to 1-2/10 with

naltrexone treatment. Similarly, we expect that patients would start at a 1-2/3 on the physician assessments (erythema and scale) and predict that the physician assessments of erythema and scale could decrease to a 0-1/3. Finally, we expect the areas of scalp involvement to remain stable over the analysis period. Based on existing data showing low number of mild side effects and no serious adverse events, we plan to enroll 75-100 patients, which is the maximum number that we would expect to see over the study period given the low prevalence of disease.

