With estimated standard deviation using a rule of thumb based on range of the scales, the anticipated 75-100 patients can achieve at least 80% power to detect mean difference of 0.7-0.8 based on patient assessment as well as 0.21-0.25 based on physician assessment. Therefore, the anticipated sample size is sufficient to detect the expected effects. The power was based on two-sided paired t-test comparing before and after treatment at significance level 0.05.

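### Background LPP/FFA drugs may be cut during the study but the model contains time only, so the before-after contrasts mix naltrexone with background reduction and cannot give a benefit specific to naltrexone

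*Combined protocol and SAP*

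**What the plan says.** Section 3.f (Prior and Concomitant Therapy) first says that patients stay on their other LPP and FFA treatments with no dose increase. It then says: "During the study period, other LPP and FFA medications may be decreased in dose or discontinued, but will not be increased or added". No condition or timing is attached to a reduction. The reason given for the rule is: "This will allow the investigators to analyze the specific benefit of naltrexone".

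E1 describes the design as "Uncontrolled open-label prospective study".

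Section G covers months 0, 3, 6 and 12 and specifies: "The longitudinal outcomes will be analyzed using mixed model analysis to account for the correlation of measures from the same subject". The effect to be tested is time: "Time effect will be assessed and contrasts will be used to compare mean difference between any two time points of interest". Section G names no covariate, cut-off, estimand or sensitivity analysis for a change in background treatment. The data collection sheet listed in L1 is not in the available text, so whether it captures such changes cannot be checked.

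**The concern.** With one arm, the change from month 0 is the only estimate of effect. Anything else that moves the scores between visits enters the same contrast. Barring increases and additions closes one route, by which new or stronger background treatment could make naltrexone look better. Allowing decreases leaves the opposite route open, and the model has nothing to separate the two.

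Three readings of the results are affected:

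- A patient who stops a background drug and holds the same score has shown a treatment-sparing benefit, but contributes zero change.
- A fade in the mean between month 3 and month 12 could be waning of naltrexone or the result of background reduction. The planned analysis cannot tell which.
- Section G expects scalp involvement to stay stable. Progression after a background drug is stopped would be read as naltrexone failing to hold the disease.

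What is at stake is the meaning of the estimate. Following the rule in 3.f and the model in G gives a different quantity from the one that 3.f promises.

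**Working it through.** **Inputs from the plan (section G).** 75-100 patients; predicted fall of 2-3 points on the 0-10 scales and 1-2 points on the 0-3 scales; two-sided paired t-test at 0.05; at least 80% power for 0.7-0.8 (patient) and 0.21-0.25 (physician). The standard deviation is described only as a rule of thumb from the scale range.

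**Step 1: reproduce the plan's figure.** Assume the SD of the change is range/4, which is 2.5 (0-10) and 0.75 (0-3). Detectable difference = SD × (1.960 + 0.842)/√n.

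- Patient: 2.5 × 2.802/√75 = 0.81; 2.5 × 2.802/√100 = 0.70.
- Physician: 0.75 × 2.802/√75 = 0.243; 0.75 × 2.802/√100 = 0.210.

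The exact t calculation gives 0.82, 0.71, 0.246 and 0.212. The stated figures reproduce.

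**Step 2: size of the background component.** Let p be the share who have reduced background drugs by a given visit and b the mean worsening that this causes. The mean change shifts by p × b. Neither p nor b is in the documents, so the ranges below are assumptions.

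| Scale | p | b | Shift p × b | Share of the smaller predicted effect |
|---|---|---|---|---|
| 0-10 | 10% | 0.5 | 0.05 | 2.5% of 2 |
| 0-10 | 30% | 1 | 0.30 | 15% of 2 |
| 0-10 | 50% | 2 | 1.00 | 50% of 2 |
| 0-3 | 10% | 0.25 | 0.025 | 2.5% of 1 |
| 0-3 | 30% | 0.5 | 0.15 | 15% of 1 |
| 0-3 | 50% | 1 | 0.50 | 50% of 1 |

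**Step 3: power.** Take the worst row on each scale with n = 75. A 2-point effect cut to 1.0 (SD 2.5) keeps 92.8% power; a 1-point effect cut to 0.5 (SD 0.75) keeps over 99%. Unequal reduction also widens the spread. On the 0-10 scale the added variance is p(1 − p)b² = 0.5 × 0.5 × 4 = 1, so the SD becomes √(6.25 + 1) = 2.69. The normal approximation is then 1.0 × √75/2.69 − 1.96 = 1.26, or about 90% power, still above 80%.

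**Step 4: does the planned model behave this way?** Simulation with n = 75, true naltrexone change −2.5, and 30% reducing from month 6 with 1 point lost each:

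- Time-only model, month-12 contrast: mean −2.17 (expected −2.5 + 0.30 = −2.20).
- With a term for reduction: −2.48.
- Adding a 0.5-point improvement not due to any drug: −2.66 (time only) and −2.96 (with the term).

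In the last case the time-only contrast overstates the true −2.5, and the added term moves it further away. The net direction therefore depends on influences that the design cannot separate, and a covariate alone does not isolate naltrexone.

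**Step 5: would stopping at first reduction repair it?** It depends on why patients reduce. These simulations also use a true change of −2.5.

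- If reduction follows recorded scores (30% reduce, 2 points lost): all-data −1.91, up-to-reduction −2.50. Over the settings tried, the standard error rises from about 0.24 to 0.25-0.34.
- If reduction follows unrecorded status between visits (26-29% reduce): up-to-reduction is about −2.2 whatever the loss; all-data is −2.5, −2.2 and −1.9 for losses of 0, 1 and 2 points.

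Neither estimate is safe alone, so both should be shown.

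**The case against.** The strongest reply is that the rule is conservative for showing improvement: it blocks the confounding that would flatter naltrexone and admits only the kind that works against it. For this one component that stands, and it is why power is not in question.

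A reader might go further and infer that the trial as a whole is biased against naltrexone, increasingly so over time. The documents do not support that. The study is open-label and uncontrolled, and 2.c recruits both existing and new diagnoses. Regression to the mean, natural fluctuation and delayed benefit from recently started background drugs would all favour naltrexone.

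A reader might also infer that a responder who cuts background drugs and relapses is indistinguishable from someone who never responded. That goes too far. Scores are taken at months 3 and 6 as well as 12, so a response present at a visit before the reduction is captured. The two look alike only if response, reduction and relapse fall between visits, or if only the 0-to-12 contrast is read.

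The size is also open to challenge. B1 calls existing treatments limited and inconsistent, so the loss on stopping them may be small; 15% reducing and losing 0.5 points gives 0.15 × 0.5 = 0.075. Nor do the documents say that patients doing well are the ones who will reduce. These points limit the claim about size and direction. They do not make the time contrast an estimate of naltrexone alone.

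**Conclusion.** The point holds as one of interpretation, and the change is cheap and worth making. Under 3.f, E1 and G together, the before-after contrasts estimate naltrexone combined with any background reduction, so the claim to isolate naltrexone's own benefit is not supported. Later visits are more exposed because reductions accumulate.

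Taken alone, the component tends to understate the effect by 0.05-1.0 points on the 0-10 scales, if 10-50% reduce and lose 0.5-2 points. On the 0-3 scales it is 0.025-0.5 points, if the same shares lose 0.25-1 point. Those shares and losses are assumptions, and the shift is zero if nobody reduces or the background drugs were not working. The net bias of the contrast, with all other influences included, has no established sign.

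A reader might set these shifts against the stated detectable differences and conclude that the sample size is inadequate. It is not: the predicted effects are large enough that power stays above 80% throughout these ranges.

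**What to change.** 1. At every visit, record the drug, date and direction of each background change, if the data collection form does not already do so.
2. In section G, keep the mixed model on all data as the main analysis and label it as the change regardless of background reduction. Beside it, add a sensitivity analysis using scores up to each patient's first reduction, and state that it assumes missingness at random.
3. Report the proportion of patients who reduced or stopped background drugs without worsening, with worsening defined in advance.
4. In 3.f, replace the sentence claiming to isolate naltrexone's benefit with a statement that an uncontrolled before-after change under these rules does not do so. Also reconcile the statement in 3.f that other treatments are continued (A1 says the same) with the permission to decrease or stop them. Which clinical rule applies is for the investigators.

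The cost is wording, possibly one line on the visit form, and one extra analysis. The sensitivity analysis will be less precise at late visits and may itself be biased if reductions follow patient status that was not recorded. Dates not collected at the visits may be hard to recover later, so the first item is best settled before data collection.

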### A2 Primary Hypothesis

Does daily oral low-dose naltrexone (3mg per day) reduce symptoms and disease progression in patients with lichen planopilaris and frontal fibrosing alopecia?

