#### 3.h Blinding of Study Drug

N/A

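### The concomitant-therapy rule is said to isolate naltrexone's specific benefit, but an uncontrolled, open-label before-after analysis cannot do that

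*Combined protocol and SAP*

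**What the plan says.** Section E3 3.f keeps patients on their existing treatment and sets a one-way rule: "During the study period, other LPP and FFA medications may be decreased in dose or discontinued, but will not be increased or added". It then states the purpose of the rule: "This will allow the investigators to analyze the specific benefit of naltrexone".

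The design is given in E1 as "Uncontrolled open-label prospective study" and in E3 3.c as "N/A: open-label, non-randomized, uncontrolled study". E2 2.d says there is no randomisation, and E3 3.h marks blinding as not applicable.

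Section G measures outcomes at months 0, 3, 6 and 12 and fits mixed models: "Time effect will be assessed and contrasts will be used to compare mean difference between any two time points of interest". Power comes from a two-sided paired t-test of before against after. The outcomes are patient-scored itch and burning/pain (0-10), physician-scored erythema and scale (0-3), and extent of scalp involvement.

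E2 2.c recruits newly diagnosed as well as established patients. The eligibility criteria in E2 2.a require no period of stable background therapy and no minimum symptom score.

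**The concern.** The sentence in E3 3.f is a claim about what the study can infer. A co-treatment rule can support it only if co-treatment is the sole other reason for scores to change. Here it is not. The disease may fluctuate, patients and physicians know that the drug is being given, and four of the planned outcomes are scores that such knowledge can influence. No control group, external comparator, run-in, repeated baseline or blinded assessor is described, so nothing in the analysis separates these influences from the drug.

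What is at stake is the conclusion that the report may draw. A significant fall shows that scores changed while patients took naltrexone plus background therapy. Read with E3 3.f, it could be reported as the effect of naltrexone itself, and no section states that limit.

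**Working it through.** **1. What the rule does and does not remove**

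| Other cause of change after month 0 | Removed by E3 3.f? |
|---|---|
| LPP/FFA drugs added or escalated during follow-up | Yes, if followed |
| LPP/FFA drugs begun shortly before month 0 and still taking effect | No; possible because new diagnoses are recruited and no stable period is required. Frequency not stated |
| LPP/FFA drugs reduced or stopped during follow-up | No; permitted, and would tend to mask benefit |
| Natural fluctuation | No |
| Patient expectation, unblinded physician rating | No |

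**2. The plan's own power figures**

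Inputs from section G: n = 75-100, two-sided alpha 0.05, 80% power, and an SD from an unspecified rule of thumb based on the scale range. I assume SD = range/4, used as the SD of the change: 10/4 = 2.5 and 3/4 = 0.75.

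Approximate detectable difference = (1.960 + 0.842) × SD/√n:
- 0-10 scales: 2.802 × 2.5/√75 = 0.81; 2.802 × 2.5/√100 = 0.70. Exact (noncentral t): 0.819 and 0.707.
- 0-3 scales: 2.802 × 0.75/√75 = 0.243; 2.802 × 0.75/√100 = 0.210. Exact: 0.246 and 0.212.

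These match the stated 0.7-0.8 and 0.21-0.25. Range/6 gives 0.47-0.55 and 0.14-0.16 and does not match. The power figures are not in dispute.

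**3. Illustration: no drug effect, assumed non-drug improvement**

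Probability of p<0.05 = P(T > t(0.975, n−1)), where T is noncentral t with n−1 degrees of freedom and noncentrality drift × √n/SD. The opposite tail is negligible. For drift 0.5 and SD 2.5 the noncentrality is 0.5 × √75/2.5 = 1.73 (n=75) and 0.5 × 10/2.5 = 2.00 (n=100).

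| Assumed drift, 0-10 scale | SD | n=75 | n=100 |
|---|---|---|---|
| 0.25 | 2.5 | 13.5% | 16.6% |
| 0.50 | 2.0 | 57.0% | 69.7% |
| 0.50 | 2.5 | 40.1% | 50.8% |
| 0.50 | 3.0 | 29.7% | 37.9% |
| 0.75 | 2.5 | 72.7% | 84.4% |
| 1.00 | 2.5 | 92.8% | 97.7% |

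On a 0-3 scale (SD 0.75), an assumed drift of 0.1 gives 20.6% and 26.1%; 0.2 gives 62.5% and 75.2%.

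**4. How much drift would explain an observed fall**

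The 95% CI half-width is t(0.975, n−1) × SD/√n. At SD 2.5 this is 0.575 (n=75) and 0.496 (n=100). To make an observed fall compatible with no drug effect, drift must reach the lower confidence limit.
- Fall equal to the detectable difference: 0.819 − 0.575 = 0.24; 0.707 − 0.496 = 0.21.
- Fall of 2: 2 − 0.575 = 1.43; 2 − 0.496 = 1.50.
- Fall of 3: 3 − 0.575 = 2.43; 3 − 0.496 = 2.50.

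On the 0-3 scales the half-width is 0.17 (n=75) and 0.15 (n=100), so a predicted 1-point fall has a lower limit of 0.83-0.85.

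The paired test stands in for the mixed-model contrasts. Both compare time points within patients, so the attribution question is the same.

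**The case against.** The strongest reply is that the sentence stands under a heading on prior and concomitant therapy and refers back to the rule. In that place, specific benefit may mean only benefit not due to added or escalated LPP/FFA drugs. This reading is the more defensible one, and the rule does serve it. But the sentence is not limited in that way, and even on this reading the rule does not cover therapy begun just before month 0.

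Second, nothing is hidden: the protocol repeatedly calls itself open-label and uncontrolled. That stands. The fault is one claim and a missing limitation statement, not a concealed or illegitimate design.

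Third, background drugs can only be reduced during the study, which would tend to work against finding a benefit. That stands for in-study changes. It does not offset the other causes by any known amount.

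Fourth, the drift values are assumed and lie near the detectable difference, where false-positive rates are bound to be high. That also stands, and the figures should be read as an illustration only.

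A reader might infer that the same attribution error runs through the whole plan. The documents do not support this. The hypothesis in A2 is put as a question ("Does daily oral low-dose naltrexone (3mg per day) reduce symptoms and disease progression in patients with lichen planopilaris and frontal fibrosing alopecia"). Section G offers a prediction ("We predict that oral low-dose naltrexone would lead to approximately 2-3 point decrease in each of the 0-10 point patient assessments") and admits that effect-size data are limited. Its power statement uses ordinary sample-size language. None of these says that the design can isolate the drug.

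**Conclusion.** The point holds for the sentence in E3 3.f. The plan claims a property that its design lacks, and no section corrects it. The rule limits confounding by other treatment. It does not make a before-after change specific to naltrexone.

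The size is conditional. With SD 2.5 (inferred from the plan's own power figures) and an assumed 0.5-point drift, 40-51% of studies with no drug effect would be significant on a 0-10 scale; across SDs of 2.0 to 3.0 the range is 30-70%. Falls of the predicted 2-3 points would need drift of about 1.4-2.5 points to be explained away. The problem is therefore most acute for falls near 0.7-0.8 points.

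A reader might go further and infer that a positive result is likely to be spurious, or that regression to the mean will inflate it. The documents support neither. They give no drift size, E2 2.a sets no minimum score that would select patients at their worst, and permitted reductions may pull the other way, so the net direction is unknown.

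**What to change.** 1. In E3 3.f, replace the specific-benefit sentence with a statement that the rule limits but does not remove confounding by other LPP/FFA treatment.
2. In section G, state that the result is before-after change on naltrexone plus background therapy and is not attributable to naltrexone alone.
3. Report each change with its 95% CI, so that readers can judge how much non-drug change would explain it.

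Optional: if the data collection form (not in the text reviewed) records recent LPP/FFA treatment changes, fix a look-back window in advance and report a sensitivity analysis in patients without such a change, keeping all patients in the primary analysis. This addresses recent background therapy only, not fluctuation, expectation or unblinded rating. If half the patients qualified (an assumption; n = 38-50), the difference detectable with 80% power would be 1.0-1.2 points on the 0-10 scales and 0.30-0.35 on the 0-3 scales, still below the predicted 2-3 and 1-2 points.

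The cost is a more modest stated conclusion. Sample size and planned tests are unchanged.

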#### 3.g Packaging

As per compounding pharmacy.

#### 3.h Blinding of Study Drug

N/A

## F Study Procedures

#### F1 Screening for Eligibility

This will be performed at a routine office visit prior to enrolling in the study.

### F2 Schedule of Measurements

Performed at 0,3,6, and 12 month office visits.

### F3 Visits

At each office visit, data will be collected as outlined on the patient assessment form. We will confirm with patients that they are not taking opioids medications and that their mood is stable without evidence of depression. Additionally, patients will be asked about any adverse reactions that they might notice from the medication, specifically inquiring about vivid dreams, nightmares, and headaches, as well as any other side effects they have noticed with the medication. The study will begin between September 1st and October 31st 2019 and continue until December 31st 2020.

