#### F4 Safety and Adverse Events

Patients will be screened at each office visit. In addition, they will be encouraged to report any concerns or issues to [name] at the contact information listed on the consent form.

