#### 4.a Definitions of Adverse Events

Reported adverse events with low-dose naltrexone are rare and mild. Vivid dreams, nightmares, and headaches have been reported with low-dose naltrexone used for other conditions. A recent case series of four patients with lichen planopilaris and a subtype, frontal fibrosing alopecia, treated with oral low-dose naltrexone at 3mg daily showed

reduction of itch, clinical evidence of inflammation of the scalp, and of disease progression. There were no reported adverse events.

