#### 4.b Data Collection Procedures for Adverse Events

All adverse events will be recorded in the patient's medical record as well as on a secure document (Excel spreadsheet in Wustl Box) and will be reviewed monthly by the study team.

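### The visit question elicits adverse events only as effects of the drug, and no cause-neutral pre-dose question on headaches, vivid dreams and nightmares is specified, so any side-effect frequency reported from this uncontrolled study would be hard to interpret

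*Combined protocol and SAP*

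**What the plan says.** The design is stated in E1: "Uncontrolled open-label prospective study". Measurements follow F2: "Performed at 0,3,6, and 12 month office visits".

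F3 gives the content of the visits. It opens with "At each office visit, data will be collected as outlined on the patient assessment form". On safety, "patients will be asked about any adverse reactions that they might notice from the medication", and the sentence goes on: "specifically inquiring about vivid dreams, nightmares, and headaches, as well as any other side effects they have noticed with the medication". F3 also has staff confirm at each visit that the patient is free of opioids and that mood is stable. Neither of those checks depends on what the patient thinks the cause is.

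The remaining safety text is short:

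- F4: besides screening at visits, patients are told that "they will be encouraged to report any concerns or issues to" a named contact.
- 4.a, headed as definitions: "Reported adverse events with low-dose naltrexone are rare and mild". It then lists effects seen elsewhere. It does not define an adverse event, a baseline or new onset.
- 4.b: "All adverse events will be recorded in the patient's medical record", and also in a secure spreadsheet that the study team reviews monthly. No limit by cause is stated.
- 4.c: patients may report in person or by phone throughout the study.
- 4.d: the reporting period is a pair of calendar dates, not tied to first dose.

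Section G names itch, burning/pain, erythema, scale and scalp involvement as outcomes. It describes no safety summary. The assessment form cited in F3 and G is not reproduced in the available text.

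**The concern.** Both halves of the F3 question are tied to the drug, so the patient has to make a causal judgement before answering. Such judgements are unreliable. Patients stay on their other treatments, which may be reduced or stopped during the study (3.f), so a new symptom has several possible explanations. An unexpected effect is also the one a patient is least likely to attribute to the drug.

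The three named symptoms raise a second difficulty. A headache or a vivid dream can occur without the drug, and 2.e itself describes the low-dose side effects as much like those on placebo. To call one of them new on treatment, one needs to know whether the patient had it before. A controlled trial could use the other arm for the background rate. Here only the patient's own pre-dose state is available, and the text does not say that it will be recorded.

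What is at stake is the safety information from the planned 75-100 patients. The protocol says that long-term safety data are lacking (2.e), and the prior evidence it cites in this disease is a series of four patients. A side-effect frequency from this study is likely to be quoted whether or not the plan promises one.

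**Working it through.** The documents give no adverse-event rate, no background symptom rate and no safety precision target, so there is no stated figure to reproduce. The check is mainly a comparison of passages.

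**Step 1: question against recording rule.** 4.b covers all adverse events. F3 asks about reactions from the medication and side effects noticed with it. The first set contains the second. Events in the first but not the second reach the record only if the patient volunteers them (F4, 4.c) or they surface through the mood and opioid checks.

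**Step 2: is there a baseline?** F2 includes a month-0 visit and F3 applies to every visit, so on a literal reading the three symptoms are raised at month 0. But a question about effects of a drug not yet taken has little meaning. No section asks for presence, frequency or severity regardless of cause before the first dose. 4.a does not define new onset, and 4.d does not tie the period to dosing.

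**Step 3: direction of the bias.** For one symptom, let

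- b = share of patients who already have it before dosing,
- s = share of those who later report it as due to the drug,
- e = share of the remaining patients who newly develop it,
- a = share of those new cases who report it as due to the drug.

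Reported share = b × s + (1 − b) × e × a. True new-onset share of all patients = (1 − b) × e.

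The first term inflates the count and a value of a below 1 deflates it. None of the four values is in the documents. The figures below are assumptions that show the mechanism; they are not estimates. Take e = 5% throughout.

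| b | True new | Reported, s = 1, a = 1 | Reported, s = 0.5, a = 1 | Reported, s = 0, a = 1 |
|---|---|---|---|---|
| 5% | 4.75% | 9.75% | 7.25% | 4.75% |
| 10% | 4.5% | 14.5% | 9.5% | 4.5% |
| 20% | 4.0% | 24.0% | 14.0% | 4.0% |
| 30% | 3.5% | 33.5% | 18.5% | 3.5% |

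Take b = 20% and N = 100 as an example. True new cases are 100 × 0.80 × 0.05 = 4. Reports are:

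- s = 1, a = 1: 100 × (0.20 + 0.04) = 24
- s = 0.5, a = 1: 100 × (0.10 + 0.04) = 14
- s = 0, a = 1: 100 × 0.04 = 4, no bias
- s = 0, a = 0.5: 100 × 0.04 × 0.5 = 2, half of the true count

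At N = 75 the first case gives 18 reports against 3 true new cases.

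**Step 4: what the plan would need.** A cause-neutral question at every visit removes the dependence on s and a. A cause-neutral question before dosing identifies b patient by patient.

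**The case against.** Three readings stronger than the documents allow are tempting.

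*A reader might infer that no pre-treatment answer will exist for the three symptoms.* The text does not establish that. Month 0 is a scheduled visit, F3 applies to each visit, and the assessment form is not available here and may carry a plain symptom item. What stands is that the available text specifies no cause-neutral question before the first dose.

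*A reader might infer that attributed reactions are the only route into the safety record.* They are not. Patients may raise any concern (F4) and report at any point during the study (4.c), 4.b sets no causal limit, and mood is checked without attribution. The three symptoms are also named to the patient, so they are prompted and not left to recall. These routes lessen the loss of unattributed events. Spontaneous reporting, however, does not give every patient a baseline.

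*A reader might infer that a planned treatment-emergent analysis is faulty.* No such analysis is planned. The aim and Section G concern symptoms, signs and scalp involvement. The weakness limits a safety summary that may be reported later; it is not an error in a stated method.

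The two harms also pull against each other. Patients who had headaches before dosing may be the least likely to blame the drug, which makes s small and the inflation slight. That is correct, and it is why no net direction should be claimed. It does not remove the problem, because without the right question s remains unknown.

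**Conclusion.** The point holds as a low-severity, inexpensive improvement. The F3 question is narrower than the recording rule in 4.b, and the available text provides no cause-neutral pre-dose question on headaches, vivid dreams and nightmares. In a study without controls, any side-effect frequency reported later could err either way. The size cannot be calculated from the documents, and the table shows only that it turns on quantities the plan does not set out to collect.

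The conclusion assumes that the assessment form adds nothing beyond the F3 wording. If it already has a neutral symptom item completed before dosing, the baseline half of the point falls away and only the wording of F3 needs attention. Nothing here affects the efficacy analysis or the sample size.

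**What to change.** 1. Reword F3 so that staff ask at each visit about any new or worsened symptom or medical event since the last visit, whether or not the patient thinks the drug caused it. Record the patient's and the investigator's view of cause in a separate field.
2. Ask about presence, frequency and severity of headaches, vivid dreams and nightmares at month 0, before the first dose, and in the same words at each later visit.
3. State in 4.a that events are described as new or worse relative to month 0, and add a line to Section G saying that they will be summarised descriptively on that basis.

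The cost is form wording, slightly longer visits and more unrelated events recorded. The month-0 item has to be in place before enrolment starts, because a baseline not taken then can be reconstructed later only from patients' memory.
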